Enrollment	Randomization	Arm 1	159 patients	Tegaderm™ on R eye, EyeGard® on L eye
		Arm 2	159 patients	Tegaderm™ on L eye, EyeGard® on R eye

2. Introduction

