5.1 Study Timelines

- Study subjects will be participating in the study for a total of 2 days.
- On day 1, study subjects will enroll in the study and undergo anesthesia with application of Tegaderm™ and EyeGard® on the eyelids. Once surgery is complete, the Tegaderm™ and EyeGard® will be removed and photograph will be taken. This will conclude participation in the study on day 1
- On day 2, study subjects will be approached by the co-investigator, [name], and will be given a patient satisfaction survey. Completion of the survey will conclude study subject participation in the study.
- We anticipate that we will be able to enroll 5 subjects per day during weekdays. Given that we plan to recruit 159 study subjects, it will take approximately 2 months to enroll all the study subjects.
- The estimated date for primary analyses will be October-December 2018.

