5.2 Procedures

- Is there a placebo control arm?

Yes No

We will perform a prospective, double-blind, randomized controlled trial. Participants will be approached by the co-investigator, [name], on the day of the surgery. The research study will be explained and potential participants will be given an informed consent form to read. After the participant has had adequate time to read through the informed consent form, think about the risks and benefits, and ask questions, he or she will be asked to sign the form if he or she wishes to participate in the study. The informed consent form will then be stored in the principal investigator's locked office. Once a study subject is enrolled, the anesthesia provider, surgical provider, as well as the nurse will be informed that this participant is part of the study. The co-investigator, [name], will then gather baseline patient demographic and clinical data.

Photographs will be taken using a digital camera at an angle parallel to the eyes (such that the camera is facing the patient directly), at a distance of 6 inches from the eyes to the lens of the camera, and will be done in the operating room with all room lights on. The photographs will be taken and cropped in such a way that both eyelids are visible but no other facial features will be recognizable. As such, photographs will not be identifiable. A disposable paper ruler will be used to determine camera distance and then placed on the patient's forehead during photography as a marker of size.

Upon entry into the operating room and prior to induction of anesthesia and prior to administering oxygen, the co-investigator, [name], will ask the study subject to close his or her eyes. The co-investigator will then take a photograph of the eyelids as a baseline assessment. Afterwards, anesthesia will be induced according to standard of care at Tufts Medical Center. Once the anesthesia provider establishes mask ventilation, the co-investigator, [name], will apply the EyeGard® on one eye and the Tegaderm™ on the other eye according to the

randomization schema. The exact time of application will be documented. At the end of the surgery, the co-investigator, [name], will remove the EyeGard® and Tegaderm™. She will then take another photograph of the eyelids and document the time.

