8.3 Number of Subjects

A previous study by Zeng et al. found that the rate of any level of eyelid erythema when using 3M Medipore is 50% while when using 3M Kind Removal Silicone Tape is 33%. We will assume that the rate of erythema with 3M Tegaderm may be similar to that of 3M Medipore and the rate of erythema with EyeGard may be similar to that of 3M Kind Removal Silicone Tape. Given that we are doing a study of matched pairs of subjects (the same study subject will undergo both treatments, one on each eye), the McNemar test is most appropriate. In order to detect a difference in erythema rates with an alpha of 0.05 and 80% power, G*Power determined that the total sample size needs to be 288 eyes, which is 144 patients. In order to account for a 10% attrition rate, we will plan on recruiting 159 study subjects.

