8.5 Randomization

Will subjects be randomized?

Yes No

In order to randomly allocate study subjects to one of three arms entirely by chance, we will use the on-line randomization tool "Research Randomizer Version 4.0, www.randomizer.org," which is a computer-based "random number generators," the numbers are generated by use of a complex algorithm (seeded by the computer's clock) that gives the appearance of randomness. This tool has been studied and validated as an adequate randomization tool, to generate a randomization list. Allocation concealment will be maintained by preparing sequentially numbered, sealed, opaque envelopes, which will contain the randomization assignment consistent with the generated randomization list.

The following strategies will be implemented in order to ensure blinding:

- (a) When a subject enrolls in the study, the co-investigator, [name], will open the envelope with randomization number inside. [name] will be the one to apply and remove the tapes. Once the tapes are removed, a second set of photographs will be taken. The dermatologists who will be in charge of determining the primary outcome (erythema score) will not be present during any part of the procedure.
- (b) The photos will only be linked to the experimental variable (tape type) by the data collection spreadsheet that is only accessible to the principal investigator, [name], and the co-investigator, [name]. After data collection for the study is complete, the photos will be presented to the dermatologists independently in a blinded manner.
- (c) Each dermatologist's grading will subsequently be recorded in the data collection spreadsheet by the co-investigator. Therefore, the dermatologist will have no opportunity to determine the type of tape used at any point during the study.
- (d) Study subjects will not be informed of which tape is assigned to which eyes, and the tape will be applied and removed while the patient is under anesthesia. Therefore, the patient will be blind to the type of tape used throughout the course of the study, including when he/she is reporting his/her satisfaction with post-operative eyelid condition.

9 Drugs or Devices

Will the research involve drugs?

Yes No

Will the research involve devices?

Yes No

10 Study Administration

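### The schema puts 159 patients in each of two arms (318) although sections 8.3 and 5.1 recruit 159 in total, and section 8.5 allocates to three arms although only two are defined

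*Combined protocol and SAP*

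**What the plan says.** The document gives the enrolment figure in three places and the number of arms in two.

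- **Study schema table (before section 2).** Arm 1 is "Tegaderm™ on R eye, EyeGard® on L eye" and Arm 2 is "Tegaderm™ on L eye, EyeGard® on R eye". Each row carries its own count of 159, and the unit printed is patients.
- **Section 8.3, Number of Subjects.** The design is within-patient: "the same study subject will undergo both treatments, one on each eye". The G*Power result is that "the total sample size needs to be 288 eyes, which is 144 patients". Then: "In order to account for a 10% attrition rate, we will plan on recruiting 159 study subjects".
- **Section 5.1, Study Timelines.** "Given that we plan to recruit 159 study subjects, it will take approximately 2 months to enroll all the study subjects", at an expected 5 subjects per weekday.
- **Section 5.2, Procedures.** The co-investigator "will apply the EyeGard® on one eye and the Tegaderm™ on the other eye according to the" randomisation schema.
- **Section 8.5, Randomization.** The paragraph on generating the list opens: "In order to randomly allocate study subjects to one of three arms entirely by chance".

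**The concern.** A patient can be in only one of the two schema arms, so the two rows add up to 318 patients. Sections 8.3 and 5.1 plan 159 patients altogether. Read literally, the schema would double enrolment with no stated reason.

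Section 8.5 names three arms. The schema defines two, and the procedure in section 5.2 leaves room for only two. That sentence belongs to the instruction for building the randomisation list and filling the envelopes, so it is operative text. A list built for three arms would contain an assignment that the protocol does not define.

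**Working it through.** **Inputs**

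- Erythema rates 50% (assumed for Tegaderm) and 33% (assumed for EyeGard), alpha 0.05, power 80%, McNemar test, attrition 10%: section 8.3.
- Two-sided testing: section 8.3 does not state the sidedness. The hypothesis in section 2.1 is non-directional, so two-sided is assumed.
- Correlation r between a patient's two eyes: not given. Independence (r = 0) is used to reproduce the plan's figure, and a range is shown below.

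**Step 1. Reproduce section 8.3.** With independent eyes, the discordant proportions are:

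- erythema under Tegaderm only: 0.50 × (1 − 0.33) = 0.335
- erythema under EyeGard only: 0.33 × (1 − 0.50) = 0.165

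The total discordant proportion is 0.335 + 0.165 = 0.50, and the ratio is 0.335 / 0.165 = 2.03. Exact (binomial) McNemar power, averaged over the number of discordant pairs, is:

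| Pairs | Power |
|---|---|
| 142 | 79.9% |
| 143 | 80.2% |
| 144 | 80.4% |

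The smallest number reaching 80% is 143. The plan's 144 therefore reproduces as a number of **patients** (pairs), and 144 × 2 = 288 eyes.

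**Step 2. Attrition.** 144 × 1.10 = 158.4, rounded up to 159. This matches section 8.3. (Dividing by 0.90 gives 160, a difference of one patient.) So 159 is the whole recruitment, not a per-arm figure.

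**Step 3. The schema.** 159 + 159 = 318 patients, or 636 eyes. 318 / 159 = 2.

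**Step 4. Timeline.** At 5 per weekday:

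- 159 / 5 = 31.8 weekdays, or 31.8 / 5 = 6.4 weeks
- 318 / 5 = 63.6 weekdays, or 63.6 / 5 = 12.7 weeks

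The stated two months is nearer the first.

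**Step 5. What each reading implies for power.** After 10% loss, 159 × 0.9 = 143 pairs and 318 × 0.9 = 286 pairs. At r = 0, 143 pairs give 80.2% and 286 give 98.2%. For other correlations, the proportion with erythema on both eyes is 0.50 × 0.33 + r × √(0.50 × 0.50 × 0.33 × 0.67). Subtracting it from 0.50 and from 0.33 gives the two discordant proportions.

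| r | Discordant proportions | Power, 144 pairs | Power, 286 pairs |
|---|---|---|---|
| 0 | 0.335, 0.165 | 80.4% | 98.2% |
| 0.1 | 0.311, 0.141 | 84.5% | 99.0% |
| 0.2 | 0.288, 0.118 | 88.5% | 99.5% |
| 0.3 | 0.264, 0.094 | 92.4% | 99.8% |
| 0.5 | 0.217, 0.047 | 98.3% | about 100% |

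No row at 286 pairs is near the 80% target that section 8.3 sets.

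**Step 6. Number of arms.** Each patient has two eyes and two tapes, with one tape per eye. The possible assignments are Tegaderm right with EyeGard left, or the reverse. These are the schema's two arms, and no third assignment is described anywhere in the text.

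**The case against.** The strongest reply is that this is editorial. Section 8.3 derives its total openly, section 5.1 repeats it, the timeline fits it, and no other section supports 318. Staff who follow the operative sections would recruit 159. The word three looks like a leftover, and nothing shows that the list or envelopes used three codes. This stands as a limit on the consequence: the primary comparison is within patients and is not at risk, and any fault in the list is hypothetical because the list is not in the documents. It does not remove the contradictions, which concern the enrolment total and the allocation instruction.

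A second reply is that the schema counts eyes: 159 patients give 159 eyes per tape and 318 eyes in all. That may be how the figure arose, but it is inference. The table says patients, and its rows are side assignments that each contain both tapes.

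A third point is that the adequacy of 159 depends on the correlation. This is correct. With negative correlation, power at 144 pairs falls to 76.3% at r = −0.1 and 72.7% at r = −0.2. Positive correlation is more plausible for two eyes of one patient, but the documents give no value. The question is separate and does not make 318 the planned number.

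Finally, section 8.5 states no allocation ratio, so an 80 and 79 split is only an illustration. What the documents support is that the arms sum to 159.

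**Conclusion.** Both contradictions hold. The schema shows 318 patients against a planned total of 159, a factor of 2, and the schema is the outlier because section 8.3's derivation reproduces as a patient total. Section 8.5 names three arms where two are defined and only two are possible.

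The sample size calculation itself is sound on its own inputs. That rests on two-sided exact testing and on independent eyes. Under independence or positive correlation, 159 recruited patients meet the stated 80% after 10% loss. The primary analysis is not threatened, but these are core design statements and should be corrected.

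**What to change.** 1. In the schema, replace the two counts with figures that sum to 159 (about 80 and 79 if allocation is meant to be equal).
2. In section 8.5, change three arms to two.
3. Confirm that the generated randomisation list has 159 entries and contains only the two side assignments in the schema, and that the envelopes match it.

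The cost is two wording corrections and one check of the list. No added patients, visits or analyses are needed to resolve this point.

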2.1 Background and Rationale

In the 1980s, taping eyes shut during anesthesia became a common practice due to the recognition of corneal abrasions as a risk of anesthesia (1). However, there is no single accepted practice of how to protect the eyes during anesthesia, and a variety of different tapes and techniques have been adopted in different institutions.

While the risk of corneal abrasion significantly decreases with the use of eye tape, patients may occasionally experience eyelid irritation from the adhesive. While the eyelid irritation is generally limited to mild erythema that resolves on its own within a day or two of receiving anesthesia, the irritation may affect patient satisfaction (2).

At Tufts Medical Center, a variety of adhesive tapes are used to shut the eyes during anesthesia, including 3M™ Tegaderm™ and the Sharn Anesthesia EyeGard®, with no preference for one or the other. While all of these products decrease the risk of corneal abrasion, none of these products have been shown to be superior to the others in terms of eyelid irritation. According to Sharn Anesthesia, “The [EyeGard®] adhesive is light enough to reduce damage to the outer eye” (3). However, there is no scientific evidence to support this claim. All we know is that the EyeGard is coated with a medical grade, pressure-sensitive acrylic adhesive and that there are no phthalates, it is latex free and silicone free.

The purpose of this study is to compare the rate of eyelid erythema after anesthesia with the use of Tegaderm™ vs. the EyeGard®. Our hypothesis is that there will be a difference in the rate of erythema between the two groups.

- Is there an active control group?

Yes No

2.2 Risks to Subjects

The risk of having Tegaderm™ or the EyeGard® placed on the eyelids is the development of skin irritation (e.g. erythema) that lasts for 1-2 days postoperatively. Given that eyelids are always shut with adhesive tape when patients undergo anesthesia, patients are already accepting these risks as part of the anesthetic. Our study does not pose any additional risks beyond those associated with getting anesthesia. The purpose of this study is to determine if one of the eye tapes results in a lower risk of skin irritation than the other.

Another risk of participating in the study is loss of confidentiality. In order to minimize that risk, all paperwork will be stored in a secure location. Furthermore, all electronic data will be held in a Tufts Medical Center provided, password protected, encrypted, Box.com storage account, which is compliant with institutional policies regarding HIPAA and the IT department.

2.3 Potential Benefits to Subjects

This study will not directly benefit participants. However, future patients undergoing anesthesia may benefit from an improved understanding of the potential erythema that may result from protective tape.

2.4 Alternatives

The alternative is not participating in the study.

3 Objectives

This objective of this study is to compare the effects of Tegaderm™ vs. EyeGard® on the eyelids during anesthesia.

- Primary Outcome:
 - The proportion of eyelids with erythema at the end of surgery after removal of Tegaderm™ vs. EyeGard®
- Secondary Outcomes:
 - Patient Satisfaction
 - Rate of Corneal Abrasions

4 Enrollment and Withdrawal

4.1 Inclusion Criteria

- Age \geq 18
- Surgeries scheduled for anesthesia of any duration

4.2 Exclusion Criteria

- Any patient that does not consent
- Any patient who has:
 - Pre-existing eyelid erythema or other eyelid trauma
 - Eyelid piercings
- Any surgery on the head, brain, neck, teeth, mouth, eyes or face
- Surgery in the prone position
- Patients <18 years old

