6.5 Provisions to Monitor the Study to Ensure the Safety of Subjects

- This study does not pose any additional safety risks beyond those associated with the application of protective tape over the patient's eyelids that occurs during standard surgical procedures. These risks include injury to the eyelid such as mild to severe erythema, edema, and abrasion. Patient safety is a top priority. If at any time a patient's safety is threatened during that patient's participation in this study, for example in the event that a patient has an allergic reaction to the tape or perhaps an unrelated surgical complication necessitates the removal of the tape, the tape will be removed and the patient will not complete his/her participation in the study.
- No Data and Safety Monitoring Board will be used in this study.

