7.1 Definitions

The study does not carry a higher risk of adverse events than typically expected from the use of tape over the eyelids during surgical procedures. Possible adverse events may include allergic reaction to the tape and abrasion caused by tape removal.

Adverse event: An adverse event is any untoward or unfavorable medical occurrence in a human subject, including any abnormal physical exam or laboratory finding, symptom, or disease, temporally associated with a subject's participation in the research.

Serious adverse reaction: a serious medical occurrence associated with the use of TegadermTM, or EyeGard[®] such as life-threatening allergic reaction.

Unanticipated problems: any incident, experience, or outcome that meets **all** of the following criteria: unexpected; related or possibly related to participation in the research; and suggests that the research places subjects at a greater risk of harm than was previously known or recognized.

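### Section 4.2 does not exclude patients with a known adhesive allergy, although the protocol names allergic reaction to the tape as a possible harm and every participant is assigned both adhesives

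*Combined protocol and SAP*

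**What the plan says.** **Eligibility.** Section 4.1 has two criteria: adult age and "Surgeries scheduled for anesthesia of any duration". Section 4.2 excludes non-consenting patients, minors, prone surgery, and surgery on the head and neck region. On the condition of the skin it lists only "Pre-existing eyelid erythema or other eyelid trauma" and eyelid piercings.

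**Harms.** Section 7.1 states: "Possible adverse events may include allergic reaction to the tape and abrasion caused by tape removal". Its example of a serious adverse reaction is "such as life-threatening allergic reaction". Section 6.5 illustrates a threat to patient safety with "for example in the event that a patient has an allergic reaction to the tape"; the tape is then removed and the patient does not complete the study. Section 2.2 describes a milder risk, which "is the development of skin irritation (e.g. erythema) that lasts for 1-2 days postoperatively", and does not mention allergy.

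**Exposure.** Section 8.3 describes the pairing: "the same study subject will undergo both treatments, one on each eye". The study schema and section 5.2 agree. Randomization decides only which eye receives which product.

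**The concern.** The protocol foresees a harm for which some patients carry a recognisable warning in their history, yet it does not ask about that history before assigning the exposure. A patient with a recorded adhesive allergy meets every written criterion. The plan responds to a reaction only once the tape has been applied.

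The stake is mainly patient safety. Section 2.1 describes several tapes in use at the centre and no single accepted practice, so in ordinary care a provider who knew of an allergy could select a product accordingly. In the trial the schema fixes both products, and no section provides for departing from it because of a patient's history. The statement in section 2.2 that the study adds no risk beyond that of anesthesia is therefore not shown to hold for these patients.

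**Working it through.** The point depends on no rate, power figure or formula, and the plan gives no figure to reproduce. The check is to follow a patient with a documented adhesive allergy through the plan and see whether any step would stop enrolment.

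1. **Inclusion (4.1).** An adult scheduled for surgery under anesthesia qualifies. Neither criterion refers to allergy or skin history.
2. **Exclusion (4.2).** The eyelid items concern the present state of the eyelid. A patient with an allergy history and normal eyelids today is not excluded.
3. **Eligibility check (10.2).** The co-investigator confirms eligibility. No further criterion is given, so the check is against 4.1 and 4.2.
4. **Baseline data (5.2).** Demographic and clinical data are gathered after enrolment. Allergy history is not named, and nothing found at this step alters eligibility.
5. **Recorded variables (8.4).** The spreadsheet list has no allergy field.
6. **Exposure (schema, 5.2, 8.3).** The patient receives Tegaderm on one eye and EyeGard on the other. Section 4.1 sets no limit on duration. Under section 5.2 a tape that falls off is replaced, with no exception for history.
7. **Safety response (6.5).** An allergic reaction leads to tape removal and the end of participation. This is the first point at which the plan takes account of allergy.

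Set side by side:

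| Section | Treatment of adhesive allergy |
|---|---|
| 2.2 Risks | Not mentioned; skin irritation is named |
| 4.1 and 4.2 Eligibility | Not mentioned |
| 5.2 and 8.4 Baseline and recorded data | Not mentioned |
| 6.5 Safety monitoring | Example of a reason to remove the tape and end participation |
| 7.1 Definitions | Possible adverse event; a life-threatening reaction is the serious example |

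No step before application would stop the patient. Consent pages and some other text are not available for review, but section 4.2 reads as a complete list, and wording in a consent form would not by itself be an eligibility criterion.

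**The case against.** The strongest reply is that the trial changes little. Section 2.1 says both products are already used at the centre without preference, section 2.2 says eyelids are always taped under anesthesia, and section 10.1 describes the tapes as part of routine care. The anesthesia, surgical and nursing staff are told of participation (5.2), and patients are monitored continuously (7.2). This stands as a limit on size: the trial adds a second adhesive and removes the choice of product. It does not supply a screen, because informal vigilance by staff is not a written criterion.

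A reader might also infer stronger points that the documents do not support:

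- **That the sections contradict each other.** They do not. Listing a possible event and saying what follows from it is compatible with an eligibility list that is silent on it.
- **That allergy is the principal foreseeable harm.** It is one of several. Section 2.2 names irritation, section 6.5 lists erythema, edema and abrasion, and section 7.1 also names abrasion.
- **That a sensitised patient must react under both tapes, giving a concordant pair that adds nothing to the McNemar test, or else be lost.** Section 2.1 describes only EyeGard's adhesive, as acrylic, and no section describes Tegaderm's. A reaction to one product alone is possible and would give a discordant, informative pair. Loss is not established either: section 4.3 keeps all subjects in the primary analysis, and the plan does not say how a patient stopped under section 6.5 would be scored.
- **That a countable number of patients or informative pairs is at stake.** The documents give no prevalence. Nor does each patient equal one informative pair. With the section 8.3 rates of 50% and 33%, the discordant proportion is 0.50 × 0.67 + 0.50 × 0.33 = 0.50 if the eyes are independent. It can lie anywhere from 0.50 − 0.33 = 0.17 to 0.50 + 0.33 = 0.83, depending on the correlation between eyes.

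**Conclusion.** The concern holds as an omission. A patient with a known adhesive allergy is eligible under sections 4.1 and 4.2 and is assigned both adhesives, although sections 6.5 and 7.1 anticipate allergic reaction to the tape. This is worth correcting before enrolment, but it is not a fatal flaw and does not threaten the validity of the primary comparison.

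Its size cannot be given as a count of patients or of McNemar pairs. The added risk is limited by routine use of both products at the centre. The conclusion rests on two assumptions: that section 4.2 is complete as shown, and that in ordinary care a provider aware of an allergy could choose another means of eye protection, which section 2.1 makes plausible but does not state.

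**What to change.** Add one exclusion to section 4.2: known or documented allergy to medical adhesive or to a component of either study product. Check it from the chart and by one history question at the pre-operative consent contact already described in sections 4.4.1 and 6.1. This aligns eligibility with sections 6.5 and 7.1.

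Keep the criterion to allergy. Excluding anyone with previous mild erythema from tape would select on the primary outcome: it would remove susceptible patients and could pull the erythema rates below the 50% and 33% assumed in section 8.3.

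The cost is one line in an amendment, one screening question and a few fewer eligible patients. The results would not extend to people with known adhesive allergy, and the report should say so. The screen will not catch an allergy that neither the patient nor the chart knows of, so the provisions in section 6.5 are still needed.
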